8.3 Statistical Methods

Descriptive statistics will be performed of all collected data except data collected only for the

purpose of data cleaning. No formal hypothesis will be tested in this study. If necessary,

Fisher's exact test, $\chi 2$ test will be used to examine differences in AEs occurrence between

subgroups (It will be defined based on the enrollment patients).

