3.1 Study Sites

This study is to select qualified hospitals which have signed contract with China Primary Healthcare Foundation as study sites. 138 target hospitals are in the charity support list. The charity will provide FIRMAGON® to patients who participate in this study. In order to ensure the representativeness of the sample, participating sites will cover all major regions across China, and China Primary Healthcare Foundation is recommended to enroll patients on a consecutive basis. The CRO will keep a record of the individuals responsible for each participating Study Site.

Ferring Pharmaceuticals (Asia) Co., Ltd.

4 Ethics

This study is an observational study where the existence of the study has no impact on the

patient except for collection of informed consent to use patients' data. Informed Consent

Form (ICF) will be reviewed and recorded by Central EC.

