This study is a multi-center, single-arm, non-interventional study among Chinese patients with prostate cancer needed androgen deprivation therapy receiving treatment with FIRMAGON®. 2500 patients who are prescribed FIRMAGON® according to clinical practice by doctors in hospitals will be enrolled in this study. This program will provide the minimum 6 doses and maximum 12 doses of FIRMAGON® to enrolled patients during one-year follow-up. Patients apply for enrollment in hospital, they will return to hospital every three months for medical assessment and other three doses of FIRMAGON® prescription during the study. 138 target hospitals are in the charity support list. The direct-to-patient pharmacy will distribute FIRMAGON to patients who are defined eligible by the doctor. The patient should bring the prescriptions and the last FIRMAGON® boxes to get other FIRMAGON®.

All enrollment patients will be followed up to collect safety information for one year from China Primary Healthcare Foundation from the 1st dose unless withdrawal of Informed Consent Form, dosing interrupted for 2 months or more than 2 months since last dose, lost to follow-up, death, or termination due to other reasons (defined in section 5.4), whichever comes first. Any AEs will be filled in Adverse Event Form (as Appendices), processing and submitting to relevant authorities.

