8.1 General Aspects

All analyses will be performed using SAS version 9.3 or above by the Biostatistician.

Numerical data are presented as number of patients, mean, standard deviation, median, min

and max. Categorical data are presented as frequency and percentage of patients. Missing data

will be analyzed as is, no imputation method will be utilized. The statistical analysis plan will

be finalized at least 1 week before the database lock.

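### For adverse event subgroups made largely of whole hospitals, such as region, the plain chi-square and Fisher tests in section 8.3 give p-values that are too small if events are correlated within hospital

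*Combined protocol and SAP*

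**What the plan says.** Section 8.3 plans descriptive statistics and adds: "No formal hypothesis will be tested in this study. If necessary", Fisher's exact or a chi-square "test will be used to examine differences in AEs occurrence between" "subgroups (It will be defined based on the enrollment patients"). No subgroup is named there, and no alpha is given.

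Section 5 describes the design: "This study is a multi-center, single-arm, non-interventional study among Chinese patients". It also sets the size: "2500 patients who are prescribed FIRMAGON® according to clinical practice by doctors in hospitals will be enrolled in this study". Section 3.1 states that "138 target hospitals are in the charity support list" and that "participating sites will cover all major regions across China".

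Section 8.1 describes how AE data will be shown: "Categorical data are presented as frequency and percentage of patients". No confidence interval is planned. The same section requires the SAP to be final at least one week before database lock. No section mentions a site effect, stratification by hospital or a robust variance.

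**The concern.** Patients at one hospital share doctors and local practice, and some of the plan's own rules make AE recording depend on these. Under section 6.1.1 an abnormal laboratory value counts as an AE when the health care provider judges it clinically significant. The study summary says that data follow current practice with no added monitoring. Section 6.3 also allows spontaneous reports. Some correlation of AE occurrence within hospital is therefore plausible, although its size is unknown.

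A geographic split is also plausible. Section 5.6 lists only two demographic items, age and domicile, and domicile will probably follow hospital closely. Section 3.1 asks for sites in all major regions, and section 1.1 stresses the difference in incidence between urban and rural areas.

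If such a split is tested as though patients were independent, differences in local reporting habit can produce a small p-value that looks like a regional difference in safety. Section 5.2 calls AE collection the main purpose of the programme, so a printed p-value is likely to be read.

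**Working it through.** There is no planned figure to reproduce. Section 8.5 takes the 2,500 from a regulatory figure, lowered after discussion with the authority, and no power, precision target or ICC lies behind it.

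**Inputs**
- Patients: 2,500 (section 5). Hospitals: 138, a target list (section 3.1).
- Mean cluster size if all enrol equally: m = 2,500/138 = 18.1.
- Event rates for illustration: 45.1% (injection site reactions), 12.7% (pyrexia) and 5.6% (fatigue), from the degarelix column of Table 1, section 1.3.
- Assumed, because the documents do not give them: ICC 0.01 to 0.10; two-sided 5% level.

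**Formulas**
- Design effect: DE = 1 + (m − 1) × ICC. Example at ICC 0.05: 1 + 17.1 × 0.05 = 1.86.
- True error of a nominal 5% test between two groups of whole hospitals: 2 × [1 − Φ(1.96/√DE)]. Example: 1.96/√1.86 = 1.44, which gives 15.0%.
- With unequal sizes (coefficient of variation CV): DE = 1 + [(CV² + 1) × m − 1] × ICC.

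**Subgroups made of whole hospitals**

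| ICC (assumed) | 0.01 | 0.02 | 0.05 | 0.10 |
|---|---|---|---|---|
| DE, equal sizes | 1.17 | 1.34 | 1.86 | 2.71 |
| True error, two groups, formula | 7.0% | 9.1% | 15.0% | 23.4% |
| Same, simulated at a 45.1% rate | 7.4% | 8.6% | 14.2% | 22.8% |
| Same, simulated at a 5.6% rate | 7.4% | 9.2% | 14.5% | 22.7% |
| Six regions of 23 hospitals, simulated at 45.1% | 9.0% | 13.8% | 30.8% | 54.6% |
| DE, size CV = 1 | 1.35 | 1.70 | 2.76 | 4.52 |
| True error, two groups, size CV = 1 | 9.2% | 13.3% | 23.8% | 35.7% |

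The simulations draw hospital rates from a beta distribution with no true subgroup difference (138 hospitals of 18 or 19 patients, chi-square test, 4,000 runs per setting).

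If only 70 hospitals enrolled (an assumption), m = 2,500/70 = 35.7. DE is then 1.69 at ICC 0.02 and 2.74 at ICC 0.05, and the two-group error is about 13% and 24%.

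**Where the plain test is sound**
- Patient-level factor spread evenly within hospitals: simulated error is 4.3% to 5.1% over ICC 0.01 to 0.10, at both the 45.1% and 5.6% rates. There is no inflation.
- The 138 hospitals compared directly with truly equal rates (2,000 runs): 5.5% at a 45.1% rate and 4.7% at 12.7%.

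**If an interval were added.** The 95% half-width for a 45.1% rate is 1.96 × √(0.451 × 0.549 × DE/2,500). Under independence it is 1.95 points. With clustering it is 2.11, 2.26, 2.66 or 3.21 points over the four ICCs.

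**The case against.** The strongest reply is that the plan claims very little for these tests. Section 8.3 disclaims any formal hypothesis and makes the tests conditional. No alpha is stated, so the 5% reference level is supplied here. Neither hospital nor region is named as a subgroup. The one separate analysis that the protocol does describe, off-label treatment in section 7.3, is a patient-level factor. Regulatory reporting under section 6.4 rests on individual cases and event clusters, not on subgroup p-values. Data are gathered through a single foundation, which may dampen differences between hospitals. The SAP is still to come and could deal with site.

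Most of this stands, and it limits the weight of the point. It does not remove the point: section 8.3 names only tests that assume independence, it leaves the subgroups open, and domicile is one of the few demographic splits available. Central collection may reduce local effects, but nothing shows that it removes them.

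A reader might infer more: that every p-value from these tests is wrong, comparisons between hospitals included, and that the reported AE rates carry intervals that are too narrow. The documents and the check do not support this. Balanced patient-level subgroups keep about 5% error. A direct comparison of individual hospitals is valid, because patients can be treated as independent given their hospital. No interval is planned, so that part applies only if one is added.

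**Conclusion.** The point holds for one class of subgroup: those made wholly or largely of whole hospitals. For these, the tests named in section 8.3 overstate the evidence whenever AE occurrence is correlated within hospital. For two groups, the true error of a nominal 5% test is about 7% to 23% over an assumed ICC of 0.01 to 0.10. This rests on all 138 listed hospitals enrolling equally, which is the favourable case: fewer hospitals, unequal sizes or several regions raise it. The actual size cannot be fixed from the documents, because they give neither the ICC nor the number of enrolling hospitals. The tests are optional and exploratory, so this is a minor improvement and not a threat to the study's descriptive results.

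**What to change.** In section 8.3 and the SAP, state that any AE comparison between subgroups aligned with hospital (region, domicile, urban/rural, hospital type) uses a Rao-Scott chi-square test or a GEE logistic model with hospital as the cluster, in place of the plain chi-square test. Keep Fisher's exact test for events too rare for this, labelled descriptive and unadjusted for hospital. Make any AE-rate interval that is later added cluster-robust. The plain tests can stay for patient-level subgroups spread evenly within hospitals.

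Keep a hospital code in the analysis export. Section 7.3 says that patients are identified there only by Study ID and patient number, and section 5.6 lists no hospital field.

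The cost is a few lines of text, standard procedures in the SAS software already specified in section 8.1, one retained variable and somewhat larger p-values where clustering exists. No new patient data are needed, and the SAP timing in section 8.1 leaves room for the change.

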8.4 Interim Analyses

No interim analyses are planned for this study.

8.5 Determination of Sample Size

In accordance with the technical requirements stipulated in "Intensive Drug Monitoring

Guidelines for Manufacturers" (Annex 2) within the opinion letter "Announcement regarding

promoting manufacturers in carrying out intensive drug monitoring work (Draft for comment)"

(NMPA Department of Drug Safety Supervisi" on Letter [2013] No. 12) issued by NMPA

Department of Drug Safety Supervision on March 25, 2013, no less than 3,000 qualified cases

or cover 80% of the patient exposure are planned to be included. Due to the low sales volume

forecast, the sample size could be decreased to 2500 patients per discussion with authority

Page 28 of 35

Intensive Drug Monitoring Protocol Version: 1.0

Date: 11-May-2020

officer. While Ferring will try the best to increase the information integrity and decrease the shedding cases.

9 Reports and Archiving of Study Documentation

A Non-Interventional Study Report based on the results obtained will be prepared and submitted to Global Research for distribution. The Final Study Report should be available within one year from collection of the last data point, and the participating sites should be informed about the results when the report is finalized.

After final database lock the Site Responsible must as a minimum store the list of participating patients and the signed Informed Consent Forms on site for 10 years. The Site Responsible should store additional study documentation for a longer period of time as required by any local regulations and/or hospital requirement.

Ferring Pharmaceuticals (Asia) Co., Ltd.

10 References

- World Medical Association Declaration of Helsinki. Ethical principles for Medical Research Involving Human Subjects, Helsinki 1964, amended in Tokyo 1975, Venice 1983, Hong Kong 1989, South Africa 1996, Edinburgh 2000, and Seoul 2008.
- 2. Epstein, M on behalf of ISPE. Guidelines for Good Pharmacoepidemiology Practices (GPP). Pharmacoepidemiology and Drug Safety 2005;14:589-95.
- 3. National Medical Products Administration. Guidelines for collection and reporting of individual adverse drug reactions. 2018.
- 4. National Medical Products Administration. Guidelines of Intensive drug monitoring for pharmaceutical manufacturers, 2013..
- National Cancer Institute. Surveillance, epidemiology, and end results program, Stat Fact Sheets: Myeloma. Accessed 16 MAR 2018. Available at: http://seer.cancer.gov/statfacts/html/mulmy.html

Add									
Add									
Add									
Add									
Add									

LABORATORY TES											
Test name	Result	Units		ference			Test date		Comm	ents	
			Lov	w	High		(dd-Mmm-yyyy)				
	`										
SUSPECT DRUG(s					 	D. C. L	04 4 1 4	01	A 41		5 44
Trade name and/or	Indication	Dose &			Route	Batch	Start date (dd-Mmm-yyyy)	Stop date (dd-Mmm-yyyy)	Action taken		Re-**
generic name. Strength, units & formulation		units	У			no. & exp. date	(uu-wiiiii-yyyy)	(du-ivimini-yyyy)		*Did the even stopping **Did the e	llenge ent abate after g the drug? vent reappear troduction?
						Add			Add	Add	Add
						Add			Add	Add	Add
						Add			Add	Add	Add
						Add			Add	Add	Add
						Add			Add	Add	Add
CONCOMITANT MI	EDICATION (6	xclude those	to treat ADF	Rs)							
Trade name and/or generic name	Indication		Strength, units &		Dose, units & frequency		Route		Stop date (dd-Mmm-yyyy)	Ongoing	
generic name		_	nulation	neq	uency			(dd-Mmm-yyyy)	(uu-wiiiiii-yyyy)	Yes	No

Intensive Drug Monitoring Protocol Version: 1.0 Date: 11-May-2020

	1	T							
Interactions (if yes,)	please inform names of t	he products in ques	tion)		·				
ADVERSE EVENT	S) (preferably a diagnos	is if not available ple	ease provide all the sy	motoms) If more than or	ne nlease enter each ever	nt on a sen	arate line	 	
Adverse		Start date	Stop date	Intensity	Outcome	Serio		Relate	dness
		(dd-Mmm-yyyy)	(dd-Mmm-yyyy)			S	s		l
						Yes	No		
				Add	Add			Ac	bb
				Add	Add			Ac	bb
				Add	Add			Ac	bb
				Add	Add			Ac	bb
				Add	Add			Ac	bb
				Add	Add			Ac	bb
				Add	Add			Ac	bb
				Add	Add			Ac	bb
				Add	Add			Ac	bb
				Add	Add			Ac	bb
				Add	Add			Ac	bb
NARRATIVE (describ using abbreviations. If pa	ne chronologically signs, s atient died, please provide	symptoms, relevant r e autopsy results).	medical history, time c	ourse and treatment of Al	DR; include laboratory res	ults of con	firmatory	procedures	without
Narrative: Regulator	y narrative? Yes □	No 🗆							

Intensive Drug Monitoring Protocol Version: 1.0 Date: 11-May-2020

1000		
Local Safety Officer comments:		
	I _	
Completed by:	Date:	Click here to enter a date
Quality control performed by:	Date	Click here to enter a date
duality control periornied by.	Date.	Click liefe to effici a date
(for Ferring LSO use only)		
Translated into English by:	Date:	Click here to enter a date
